3.0 What is/are the hypothesis(es)?

1. 26% of RA patients will flare after TJR, defined as
 - a. Post op increases in DAS28 > 1.2 if baselines < 3.2 or > 0.6 if baseline ≥ 3.2 OR
 - b. Are worse or much worse on question rating their RA since pre-surgery AND
 - c. Have at least one of
 - i. Want / need treatment
 - ii. An increase in MD Global of 2/10
 - iii. An increase in Patient Global of 2/10 (according to the definitions noted above)
2. The OMERACT preliminary flare questions (PFQs) will detect patients who flare as defined above.
3. RA patients who flare after TJR have worse baseline pre-operative disease activity (DAS >3.2), worse baseline function (HOOS, KOOS, HAQ, elbow/shoulder surveys) and more likely will have had a history of withdrawing a biological therapy compared to patients who do not flare.
4. RA patients who flare post op will not meet their physical therapy milestones and will have worse HOOS, KOOS, elbow, or shoulder pain and function outcomes 1 year after arthroplasty.
5. RA patients who flare will exhibit enhanced immune activation when baseline levels are compared to levels in patients who flare within 6 weeks of surgery based on increased expression/activation of ROCK, IRF4, IRF5 and IRF8 and decreased expression/activity of their inhibitors (Def6 and SWAP-70). These molecules participate in a biologic pathway that regulates production of pro-inflammatory cytokines, potential mediators of RA flare.
6. There is a discrete set of genes expressed in circulating monocytes in RA patients during flare and prodrome of flare.

4.0 Identify and define the primary outcome and when the outcome will be measured. If measuring change in post-operative function is the most important, that will be your primary outcome.

The primary outcome is rate of RA flare within 6 weeks of surgery as measured by the OMERACT flare questionnaire.

5.0 Identify and define the secondary outcome(s) and when they will be measured (list additional goals one at a time with their corresponding outcomes).

1. The severity and impact of flares, using the OMERACT PFQs in the post arthroplasty setting: PFQs including flare intensity, duration of flare and worsening of domains associated with flare (pain, fatigue, stiffness, patient

- reported tender and swollen joint count, difficulties with coping and participation).
- 2. DAS28 at baseline and post-op week 6, and the change during this interval.
- 3. RAPID 3 weekly for 6 weeks and every 3 months for 1 year after arthroplasty, DAS-28, HOOS, KOOS, shoulder/elbow survey, patient global at baseline, 6 weeks, and 1 year.
- 4. Physical therapy functional milestones (PT questionnaire) at baseline and weekly for 86 weeks.
- 5. Biological markers of immune activation including levels of IRF4, IRF5, IRF8, IBP/Def6, SWAP-70, ROCK1, ROCK2 in synovial tissue taken at surgery. Levels of the same immune biomarkers in the peripheral blood measured pre-operatively, at 6 weeks post-operatively and at one year post-operatively.
- 6. Measurement of discrete set of genes expressed in circulating monocytes in RA patients obtained at baseline and weekly for 6 weeks after surgery in a subset of patients at high risk for flare (based on patients who withdrew biologics)

[Help](#)

ID: 2014-233

View: 2.1 Background

[Help](#)

BACKGROUND - Be sure to answer each question individually

1.0 Explain why these research questions are being asked:

RA patients who undergo arthroplasty have severe erosive disease; preliminary data suggests a flare rate as high as 26% in the post-operative period. This study would confirm the rate of post-operative flare, and evaluate the clinical and biologic factors which predict flare. We would also look at the impact of flare on arthroplasty outcomes (HOOS, KOOS, elbow/shoulder survey) and RA disease status (HAQ, DAS-28, RAPID) and better understand the biology of flare.

Flare after arthroplasty is clinically relevant, as medications are typically withheld at the time of surgery with the aim of diminishing surgical site infections.

However, patients who flare may not be able to adhere to post-operative rehabilitation regimens, leading to worse functional outcomes. In addition, patients who flare may have difficulty achieving remission or low disease activity when medications are re-started, leading to worse disease outcomes. There is little information about the characteristics and outcome of flare in the post-operative period. Better understanding of the incidence and clinical characteristics of post-operative flare and the means to predict who will be most likely to flare could lead to more tailored management strategies and potentially better arthroplasty and disease outcomes.

By gathering longitudinal clinical and biologic data from RA patients and obtaining blood and tissue taken at the time of arthroplasty, we have the ability to better characterize precursors and descriptors of flare by comparing patients who flare to those who do not flare. Moreover, the characteristics and outcomes of flare in the post-operative period may be generalizable to understanding the biology and predictors of flare in RA.

2.0 What is the background of the topic that you believe is important for the reviewer to know in considering this protocol, including prior studies by this research team.

Describe strengths and deficiencies of prior studies; explain how this study fits in. Include references.

While the proportion of total arthroplasties performed on RA patients has decreased, the rates of arthroplasty for RA remains stable (Mertlesman-Vos ACR 2012). In spite of improvements associated with the widespread use of potent disease modifying drugs (1, 2), 30-58% of patients with RA can expect to undergo arthroplasty over the course of their illness (3, 4). Therefore a large number of RA patients are affected by perioperative management decisions.

Little is known about the characteristics or rate of flare in the post-operative period, and little is known about the impact of post-operative flare on either overall disease status or arthroplasty outcome. We have shown that RA patients who undergo THR have worse outcomes at two years in WOMAC pain and function scores compared to OA controls ([name] EULAR 2013), but the reasons for this disparity are not understood. To minimize risk of infection, biologic agents are discontinued perioperatively. It is not known if increases in flare contribute to worse THR outcomes in RA patients relative to OA patients but post-operative flare needs to be considered as a likely factor. If RA patients who flare are unable to participate in postoperative rehabilitation regimens which are important in optimizing arthroplasty outcomes, they may not achieve optimal outcomes. In particular domains that worsen with flare such as fatigue and difficulty coping and participating, conceivable could contribute to a worse outcome. Paradoxically, while patients with multiple arthritic joints have worse outcomes after arthroplasty compared to patients with a singly affected joint (5), which may explain the worse outcome for RA THR patients, RA TKR patients do equally well as osteoarthritis controls, ([name] EULAR 2013). Thus factors other than polyarticular joint involvement must be impacting outcomes in RA patients undergoing THR. RA patients who have a prolonged or difficult time in re-establishing low disease activity or remission may have worse arthroplasty outcomes and this may be associated with worsening of the flare domains of joint pain and swelling, reflected by escalation to polyarticular disease (6, 7).

Tools are being developed to define and identify flare. Domains such as worsening of patient global assessment, increasing joint pain and swelling, worsening fatigue and pain; difficulty coping and participating, increased patient-reported specific areas of joint pain and swelling, as well as increased medication use have been identified as important in RA flare in general (8). However, the characteristics of post-operative flare have not been studied or defined. Preliminary data from the CATCH cohort (submitted) suggest flare rates of 19-45% occur as part of the course of disease, depending on the flare definition used, even without withdrawing therapy. Data from the NORDMARD registry (9) using a combination of patient reported worsening and treatment increase was associated with a mean (SD) DAS28 worsening of 1.96 (1.28) indicating that a worsening of the DAS28 of 1.2 or by 0.6 if the baseline is already 3.2 is a valid definition of flare as published by van der Maas et al. (10) and that the two definitions of flare are linked. Further assessments of these definitions of flare are required in different patient populations. Validating a tool to identify flare in the post arthroplasty setting would improve the ability to detect flare earlier and implement means to abrogate the impact of disease worsening to enhance long term outcomes for overall disease as well as for arthroplasty.

If this study confirms the high rate of flare in the post op period using a patient reported tool, we will better understand operative features and clinical and biological predictors of flare which will ultimately enable us to identify modifiable risk factors. The ability to predict which patients are likely to flare would be useful in optimizing overall treatment goals and surgical outcomes. Current clinical algorithms for monitoring disease activity are excellent tools for monitoring disease status, but are not completely adequate for identifying and predicting flare and may

not identify all factors that influence the post-operative course. For instance, if RA patients experience worsening pain, stiffness, and fatigue in the post operative course they may not adhere to or benefit from rehabilitation interventions in the same way that usual arthroplasty patients do. These factors have not been studied in the post-arthroplasty setting.

Collecting specimens longitudinally from a cohort of well characterized RA patients with high likelihood of worsening disease activity and post-operative flare provides a unique opportunity to study the biology of RA worsening in the context of clinical domains associated with RA disease activity and flare. It is well known that deregulation of immune responses plays a major role in many autoimmune diseases like RA. Delineating the molecular mechanisms which control the development, activation and differentiation of immune cells could lead to better understanding of how they become deregulated in disease states including RA, with particular focus on a set of molecules that are important in controlling the activation of immune cells. These molecules include IRF4, IRF5, IRF8, IBP/Def6, SWAP-70, ROCK1, ROCK2, and signaling molecules involved in responsiveness to activation stimuli. We hypothesize that in those RA patients who flare after arthroplasty there will be increased ROCK activation leading to enhanced activity of IRF4 (as well as IRF8 and possibly IRF5) and increased expression of pro-inflammatory cytokines/chemokines such as IL-17, IL-21 and CCL20. By following the levels to of ROCK pathway molecules longitudinally we can determine the relationship of these molecules to states of disease activity.

Patients managed with TNF inhibitors who discontinue the medication provide a unique opportunity to study the biology of flare in RA. An unbiased, bioinformatics approach to patient assessment is a useful strategy for identifying defects in complex pathways that result in RA disease activity. Transcriptomes from purified populations of peripheral blood mononuclear cells (CD4+, CD8+, CD20+, CD14+, CD56+) will be compared from samples harvested from patients who flared to those who did not flare during follow up.

Many patients with RA who flare describe non-specific prodromal symptoms such as intense fatigue and flu-like symptoms. These may represent manifestations of a cytokine storm that is triggered by unknown antecedents. Instruments to measure flare such as the OMERACT PFQs have been very recently developed and validated to provide a new opportunity to correlate molecular findings with clinical signs and symptoms of flare. Patients managed with TNF inhibitors who discontinue the medication perioperatively are most likely to be at increased risk for flare and provide a unique opportunity to study the biology of flare in RA. The goal of this aim is to correlate the clinical phenotype as measured by the OMERACT PFQ, measured weekly with the immunological data. The immunological phenotype will be characterized using RNA sequencing of white blood cell (WBC) to develop a comprehensive molecular profile of RA flare.

Comparison of data collected in patients who flare versus those who do not flare provides a unique opportunity to characterize and understand flare, and define the significance of perioperative flare on arthroplasty and disease outcomes while providing further understanding of the biology and immunology of RA worsening.

2. Pincus T, Sokka T, Kautiainen H. Patients seen for standard rheumatoid arthritis care have significantly better articular, radiographic, laboratory, and functional

status in 2000 than in 1985. *Arthritis Rheum* 2005; Apr;52(4):1009-19.

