1.0 What is the condition or intervention to be studied?

The condition to be studied is worsening (flare) of rheumatoid arthritis (RA) in patients who have undergone arthroplasty. RA patients undergoing arthroplasty most often have severe, erosive disease. If the rate of flare approaches the estimated 26% rate suggested in a previous study for RA patients after arthroplasty (*Johnson ACR 2011*), this could be of significance in regards to their long term arthroplasty and disease outcomes. Patients who flare may not be able to participate in the post-operative rehabilitation thought necessary for optimal arthroplasty outcomes, and it may be difficult for patients who flare after

*Please click
Here for
example.*

discontinuing immunosuppressant medications for surgery to regain remission or low disease activity. Detailed clinical data collected longitudinally from RA patients with severe erosive disease undergoing arthroplasty in conjunction with further characterization of the molecular profile of blood and operative tissue could provide valuable information to inform best practices for this patient group.

2.0 What is/are the research question(s)/specific aim(s)? Pose very specific questions that can be addressed within the proposed design of the study. Prioritize them in order of importance.

1. To determine the rate of post-operative RA flare within 6 weeks of surgery, defined as
 - a. Worsening of disease activity, defined as an increase in the DAS-28 by 1.2 or by 0.6 if the DAS28 was ≥ 3.2 , OR
 - b. Patient reported worsening, defined as noting they are worse or much worse on the question rating their RA since pre-surgery
 - c. AND one of:
 - i. patient wants/needs retreatment of DMARDs and/or biologics and/or prednisone increase (or Medrol dose pack or equivalent or intra-articular corticosteroid injection)
 - ii. increase in MD global of 2/10
 - iii. increase in patient global of 2/10 (on the OMERACT Preliminary Flare Questions [PFQ])
 - iv. flare severity score of ≥ 10
2. To evaluate the responsiveness of the OMERACT PFQ in patients who flare, as defined as a worsening of DAS-28 by 1.2 or by 0.6 if the DAS28 was ≥ 3.2 OR by patient reported worsening.
3. To determine predictors of post-operative flare within 6 weeks of surgery such as baseline disease activity measures and biomarkers, including molecules in the Rho associated kinase (ROCK) pathway, which are measures of immune system activation

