Pending the distributions of the data, in aim 2 we will evaluate the standard mean difference or effect size for each domain (WOMAC, DAS-28, Flare questionnaire (pain, Pt global, stiffness, fatigue, coping, participation, Pt reported TJC, SJC) in patients who flare vs. those who do not based on criteria of DAS28 worsening, patient reported worsening, MD global, need to initiate or escalate treatment. We would also explore differences in long term WOMAC scores and biomarkers stratifying by flare and adjusting for unknown confounders including baseline function, age, sex, and co-morbidity score. Standard statistical tests will be used.

In aim 3 we will examine a limited number of predictors of flare within 6 weeks using appropriate statistical methods by using a generalized estimating equation and will adjust for unrecognized confounders/effect modifiers including long term WOMAC scores, baseline function, age, sex, and co-morbidity score, and biomarkers stratifying by flare. Standard statistical tests will be used.

In aim 4 we aim to determine how patients who flare meet physical therapy milestones including walking distance, and ADLs, in comparison to patients who do not flare. The evaluation of meeting physical therapy milestones is exploratory. Physical therapy milestones are routinely evaluated as post-op TJA measures and are done weekly. We will examine the distributions of change for each covariate recorded by physical therapy and compare changes in each domain stratified by flare vs. no-flare.

A potential analytic plan depending on distribution of the final data to assess PT milestones will include:

Physical therapy milestones will be assessed based on the questionnaire and analyzed as outlined below: patient VAS: continuous variable- ranging from 0 ~100, analyzed with T-test or regression

Change will be analyzed by

- 1- ANCOVA and study of change
- 2- GEE and treat delta as our continuous outcome

Walking distance: Ordinal variable - Chi-square, fisher exact

Stairs/Transfers/Activities/Driving/Employed: Nominal- Chi-square, fisher exact

We will also explore whether or not the meeting of PT milestones impacts pain and function at 1 year using the HOOS/KOOS. We will treat PT milestones as a binary and WOMAC outcomes will be analyzed as predictors.

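### Hypothesis 3 tests baseline DAS28 above 3.2 as a predictor of a flare whose DAS28 threshold halves at that same value, so the association is partly set by definition and its direction is unknown

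*Combined protocol and SAP*

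**What the plan says.** Under Specific Aims, item 2.0, Aim 1 counts as disease worsening "an increase in the DAS-28 by 1.2 or by 0.6 if the DAS28 was" at least 3.2. Item 3.0, Hypothesis 1 repeats the rule: "Post op increases in DAS28 > 1.2 if baselines < 3.2 or > 0.6 if baseline" is at least 3.2. Criterion b is the patient's own rating of worse or much worse since before surgery. Criterion c requires one further sign, from four alternatives in Aim 1 and three in Hypothesis 1.

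Hypothesis 3 states "RA patients who flare after TJR have worse baseline pre-operative disease activity (DAS >3.2", closing the bracket there, and adds that these patients "more likely will have had a history of withdrawing a biological therapy compared to patients who do not flare".

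On biologics, criterion c.i in Aim 1 is that the "patient wants/needs retreatment of DMARDs and/or biologics and/or prednisone increase" (steroid pack and joint injection also count). The Background, item 2.0, says "To minimize risk of infection, biologic agents are discontinued perioperatively".

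Two other statements bear on the point. Item 4.0 gives a different outcome: "The primary outcome is rate of RA flare within 6 weeks of surgery as measured by the OMERACT flare questionnaire". The analysis section (2.11.1, item 3.0) says "In aim 3 we will examine a limited number of predictors of flare within 6 weeks", using generalized estimating equations with adjustment for function, age, sex, co-morbidity, WOMAC scores and biomarkers. It does not mention that a predictor overlaps the outcome definition.

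**The concern.** A patient at 3.2 or above needs half the DAS28 rise that a patient below 3.2 needs. If both groups changed by exactly the same amounts, the higher group would still meet criterion a more often, and Hypothesis 3 would appear confirmed. Covariate adjustment cannot remove a link made by the outcome definition.

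Regression to the mean works against this. Patients selected for a high baseline tend to fall and those with a low baseline tend to rise, which lowers the flare frequency in the high group. The observed association would mix a definitional push, a statistical pull and any true effect, and the plan has no means of separating them.

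The Background wants predictors as modifiable risk factors or signalling biomarkers for later validation. A predictor produced or hidden by the definition would misdirect that work.

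**Working it through.** **The plan's own figure.** The sample size concerns the flare rate, not the predictors. The two-sided exact binomial test with N = 47, P0 = 0.26 and P1 = 0.10 rejects at 6 or fewer or 19 or more flares, with actual alpha 0.0445 and power 0.8143, as printed. Nothing here disputes it. The plan gives no figure for the Hypothesis 3 comparison.

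**Inputs.** From the documents: thresholds 0.6 and 1.2, switch point 3.2. The only SD of DAS28 change is 1.28 (Background), from registry patients who had already worsened by a mean of 1.96, so it is not an estimate for this cohort. Everything else is assumed: mean change 0; SD of change 0.8 to 1.5; or, for step 2, SD 1.3 at both visits, mean 3.5 or 4.0, and correlation 0.5 to 0.9.

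**Step 1: criterion a alone, change independent of baseline.** P(meets a) = 1 − Φ(threshold / SD).

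| SD of change | Baseline < 3.2: P(rise > 1.2) | Baseline ≥ 3.2: P(rise > 0.6) | Odds ratio |
|---|---|---|---|
| 0.8 | 6.7% | 22.7% | 4.1 |
| 1.0 | 11.5% | 27.4% | 2.9 |
| 1.28 | 17.4% | 32.0% | 2.2 |
| 1.5 | 21.2% | 34.5% | 2.0 |

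For example, at SD 1.0: (0.274/0.726) / (0.115/0.885) = 2.9.

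Under the same assumption (SD 0.8 to 1.28, 65% of patients assumed at 3.2 or above), Fisher's exact test at nominal 0.05 rejects in 13–17% of simulated studies at N = 47 and 33–54% at N = 109. With equal rates in the two groups it rejects in 2.7–4.5% across N = 47 to 200.

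Criteria b and c dilute the effect without removing it. One simulated composite at SD 1.0 gave 13.9% v 20.8% (OR 1.6) if read as (a or b) and c, and 15.2% v 28.5% (OR 2.2) if read as a or (b and c).

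**Step 2: criterion a alone, with regression to the mean.** Baseline B and week 6 F are bivariate normal with equal means and SD 1.3, so SD of change = 1.3 × √(2(1 − ρ)). The frequencies are P(F − B > 1.2 | B < 3.2) and P(F − B > 0.6 | B ≥ 3.2), by numerical integration. Mean 3.5 is shown, with the odds ratio at mean 4.0 in the last column.

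| ρ | SD of change | Baseline < 3.2 | Baseline ≥ 3.2 | OR | OR, mean 4.0 |
|---|---|---|---|---|---|
| 0.9 | 0.58 | 3.0% | 11.6% | 4.2 | 4.1 |
| 0.8 | 0.82 | 11.5% | 16.7% | 1.5 | 1.5 |
| 0.7 | 1.01 | 19.2% | 18.7% | 0.97 | 0.94 |
| 0.6 | 1.16 | 25.6% | 19.5% | 0.70 | 0.68 |
| 0.5 | 1.30 | 31.0% | 19.7% | 0.55 | 0.53 |

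The direction therefore depends on a correlation the plan does not give.

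**Step 3: one common DAS28 threshold.** In the model of step 2, a threshold of 1.2 for everyone gives 19.2% v 6.5% at ρ = 0.7 (OR 0.29). Over ρ = 0.9 to 0.5 the odds ratio runs from 0.41 to 0.21. A common threshold of 0.6 gives 0.52 to 0.23. It is a reverse bias throughout.

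**Step 4: biologic withdrawal.** This was simulated with no true effect of withdrawal and SD 1.0, first for patients who did not withdraw, then for those who did.

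| Share of withdrawers meeting c.i by restarting | (a or b) and c | a or (b and c) |
|---|---|---|
| All | 18.3% v 27.1%, OR 1.7 | 23.8% v 27.0%, OR 1.2 |
| Half | 18.3% v 22.8%, OR 1.3 | 23.9% v 25.3%, OR 1.1 |
| None | no difference | no difference |

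Other assumed frequencies for b and c widen the range to about 1.0–2.1.

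**The case against.** **The threshold is deliberate.** The Background cites the baseline-dependent rule as a published and valid flare definition. That supports using it for the flare rate. It does not support testing its switch point as a risk factor for the flare it defines.

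**The analysis is exploratory and small.** The plan calls all secondary outcomes exploratory, and at N = 47 false rejection is only 13–17% even without regression to the mean. This lowers the stakes, but exploratory predictors are what the study intends to carry forward.

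**The questionnaire may define the outcome.** If item 4.0 governs, the DAS28 switch does not enter. That stands as a limit. Hypothesis 1 nevertheless states flare as the composite, so the two definitions must be reconciled.

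**The bias need not be upward.** A reader might infer that the definition is bound to produce a positive finding. That holds only if change is independent of baseline. At correlations of 0.7 to 0.5, which correspond to SDs of change of about 1.0 to 1.3, the odds ratio is null or reversed.

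**Biologic withdrawal.** A reader might also infer that withdrawal is built into the flare definition, so that routine resumption raises the primary rate. The documents do not show this. Withdrawal appears in neither a nor b. It could enter only through c.i, one of several alternatives, only if planned resumption is read as wanting or needing retreatment, and only for a patient who also meets a or b (b alone on the second reading). c.i covers other drugs too, so patients with no held biologic can meet it. Hypothesis 3's wording could also mean past discontinuation. This is an undefined term, not a demonstrated error.

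**Conclusion.** The point holds for baseline DAS28 wherever the composite defines flare. The predictor's cut-point coincides with the outcome's threshold switch (they differ only for a patient at exactly 3.2), and the planned adjustments do not address it. With no true association, criterion a alone can give an odds ratio anywhere from about 4 to about 0.5 over plausible correlations, so an observed positive, null or inverse result would not answer Hypothesis 3. The overlap itself needs no assumption. Its size and sign rest on assumed SDs, means and correlations and a normal model.

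For biologic withdrawal only a conditional ambiguity remains, with an odds ratio of about 1.0 to 2.1 depending on how c.i, the OR/AND grouping and the other inputs are taken. The flare rate and its sample size calculation are not challenged. This is a change that should be made, not one that stops the study.

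**What to change.** 1. Keep the composite for estimating the flare rate. State its OR/AND grouping, and reconcile Hypothesis 1 with item 4.0 so that one definition governs.
2. For baseline DAS28 as a predictor (Aim 3, Hypothesis 3), make the main outcome patient-reported worsening plus c, without the DAS28 threshold. Report the composite as a sensitivity analysis and state the overlap beside it. Some regression to the mean may remain through the global-score changes in c, but no cut-off then depends on baseline DAS28.
3. For the other predictors, add week-6 DAS28 as a continuous outcome adjusted for baseline DAS28. This does not serve for baseline DAS28 itself.
4. Do not replace the split rule with one DAS28 change threshold for everyone (step 3).
5. State whether planned resumption of a held drug counts under c.i, and repeat the withdrawal analysis without c.i. This concerns what is counted, not what patients receive.

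Cost: analysis wording and one extra derived flare variable, from items the flare definition already requires. The downside is that the main outcome for this one predictor becomes less comparable with the rate analysis and with work using the composite.
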